### NCSS 8.0 Two Proportions Report

Dataset Untitled Zero Adjustment Method: None Note: Exact tests and c.i.'s were not run because total count > 50 (specified under 'Reports' tab).

#### **Table Section**

				N1	N2	M1	M2	Ν
Α	В	С	D	(A+C)	(B+D)	(A+B)	(C+D)	(N1+N2)
65	39	38	65	103	104	104	103	207

#### **Confidence Intervals of Difference (P1-P2)**

Interval	Estimated	Confidence	Confidence
Method	Value	Limit	Limit
Chi-Square (Pearson)	0.2561	0.1456	0.3666

(The calculation results are presented in the language of the original source, i.e., from NCSS 8 statistical program).

- This is a non-inferiority trial; therefore, a non-inferiority margin for the primary endpoint should be justified and amount to not more than 14.5%.
- An expected rate of positive response to therapy (absence of a sore throat as an efficacy measure) in a comparator drug arm is 63%.
- An expected rate of positive response to therapy (absence of a sore throat as an efficacy measure) in a study drug arm is 65% (chosen within the tested hypothesis and based on the sample size and expected positive response).
- A one-sided type I error ( $\alpha$ ) = 2.5 % (0.025)
- A type II error ( $\beta$ ) = 20% (0.2), which corresponds to 80% power.
- Expected discontinuation from the trial will amount to 10% during the treatment.

The tested hypotheses are worded as follows:

1. Null hypothesis (Ho): Difference in the primary endpoint achievement incidence while using Angal, the study drug, and ANTI-ANGIN® FORMULA, the original drug, for treatment of acute infectious and

inflammatory pharyngeal diseases will exceed 14.5% in favor of ANTI-ANGIN  $^{\circledast}$  FORMULA:

$$H_0: p_1 - p_2 \le -0.145$$

2. Alternative hypothesis (HA): Difference in the primary endpoint achievement incidence while using Angal, the study drug, and ANTI-ANGIN® FORMULA, the original drug, for treatment of acute infectious and inflammatory pharyngeal diseases will not exceed 14.5% in favor of ANTI-ANGIN® FORMULA

$$H_A: p_1 - p_2 > -0.145$$

Where p1 and p2 is the primary endpoint achievement incidence while using Angal, the study drug, and ANTI-ANGIN® FORMULA, the original drug, respectively.

To calculate a sample size in every group, one can use a formula presented by Chow S, Shao J, Wang H. 2008. Sample Size Calculations in Clinical Research. 2nd Ed. Chapman & Hall/CRC Biostatistics Series. page 90:

$$n = (p_1 \times (1 - p_2) + p_2 \times (1 - p_2)) \times \left(\frac{z_{1-\alpha} + z_{1-\beta}}{p_1 - p_2 - \delta}\right)^2$$

where:

- n = Size of one group;
- z = Normal distribution function at the set levels of  $\alpha$  and  $\beta$ ;
- $\delta$  = Non-inferiority margin;
- p1 = Expected proportion in Angal group;
- p2 = Expected proportion in ANTI-ANGIN® FORMULA group.

Substituting the above data into this formula, we obtain a minimal number of patients in every group without account for withdrawal: 128 patient completed the trial (total 256 patients).

In view of the expected discontinuation from the trial during the therapy of 10%, not less than 280 patients are required for randomization (140 patients in each group).

The calculation results by the above formula were also checked using nQuery, a validated program (see below), and considered to be identical.

	1	2	3	4	5	6	1
Confidence level, 1-cc (one-sided)	0.975						
Standard propertion, # s	0.630						
Test expected proportion, #+	0.650						
Lower limit for $\pi_{\pi} \cdot \pi_{g}$ . LL	-0.145						
Number of simulations	1000						
Random seed for simulations	2345						
Power (%)	80						
	128						

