# 1. Protocol synopsis

Trial title	A Prospective, Multicenter, Open, Randomized, Parallel Clinical Trial for Comparative Assessment of Efficacy and Safety of Angal, Lozenges [Menthol], 1  mg + 5  mg (Sandoz d.d., Slovenia), and ANTI-ANGIN ® FORMULA, Lozenges, 0.2  mg + 2  mg + 50  mg (OOO Valeant, Russia) in Treatment of Patients with Uncomplicated Acute Infectious and Inflammatory Diseases of the Pharynx Accompanied by a Sore Throat
Trial code	TE_004_ANG_LOZ
Sponsor	ZAO Sandoz
Study drug	Angal, lozenges [menthol], containing 1 mg of lidocaine hydrochloride and 5 mg of chlorhexidine dihydrochloride
Reference drug	ANTI-ANGIN ® FORMULA, lozenges, containing 0.2 mg of tetracaine hydrochloride, 2 mg of chlorhexidine diacetate, and 50 mg of ascorbic acid
Clinical trial phase	
Trial population	Up to 280 patients are planned to be included (randomized) into the trial (140 patients in every treatment arm) with probable withdrawal of not more than 10% patients during the trial. A minimal number of patients required for the statistical analysis is 256 (128 patients in every treatment arm) provided that they completed the trial according to the protocol.
Scheduled trial duration	Not more than 7 days: Screening/randomization/initiation of trial therapy: Day 1. Therapy duration: up to 5 days depending on the trial arm. A follow-up visit (on the phone): 2 days after the last scheduled visit to the trial site. Total enrollment duration: 8 months.
The number of trial sites	up to 20

Trial objective	This trial has been designed to evaluate the non-inferior therapeutic efficacy and safety of the study drug Angal, lozenges [menthol] 1 mg + 5 mg (Sandoz d.d., Slovenia), comparing to ANTI-ANGIN ® FORMULA, lozenges, 0.2 mg + 2 mg + 50 mg (OOO Valeant, Russia), in treatment of patients with uncomplicated acute infectious and inflammatory diseases of the pharynx accompanied by a sore throat.

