#### 4.2.4.6 Visit of premature discontinuation of the trial

Visit 2 procedures will be applied for the visit of premature discontinuation.

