#### 5.3.3 Replacement of the excluded subjects

Replacement of the excluded patients during the trial is not envisaged.

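### Protocol 9.2: the sample-size formula gives 133 per arm, not the stated 128, and 10% loss from 280 leaves 252 completers against a stated minimum of 256

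*Protocol*

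**What the plan says.** Protocol 9.2 (Planned number of subjects) assumes 65% without sore throat on Angal and 63% on the comparator, a margin of −0.145, one-sided alpha 0.025 and 80% power. It cites a textbook formula and reports: "Substituting the above data into this formula, we obtain a minimal number of patients in every group without account for withdrawal: 128 patient completed". It then says that the formula results "were also checked using nQuery, a validated program (see below), and considered to be identical". The nQuery table shows 128 at one-sided confidence 0.975, from 1000 simulations.

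On losses, 9.2 says: "Expected discontinuation from the trial will amount to 10% during the treatment". From that it concludes that "not less than 280 patients are required for randomization (140 patients in each group" are needed. The synopsis (Trial population) plans up to 280 "with probable withdrawal of not more than 10% patients during the trial", and says that the minimum for analysis "is 256 (128 patients in every treatment arm) provided that they completed the trial according to the protocol". Section 5.3.3 adds: "Replacement of the excluded patients during the trial is not envisaged".

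**The concern.** There are two separate faults in the same calculation.

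- **The stated result and its check.** A reader who puts the stated inputs into the stated formula does not get 128. The formula and the software therefore do not agree, although that agreement is the only verification the protocol offers for its sample size.
- **The allowance for losses.** At the loss rate the protocol itself expects, 280 randomised patients do not yield the number of completers it calls the minimum, and excluded patients are not replaced.

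The stake is a sample-size justification that cannot be reproduced and a stated minimum that the enrolment does not secure. It is not a seriously underpowered trial.

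**Working it through.** **Inputs** (Protocol 9.2): p1 = 0.65, p2 = 0.63, δ = −0.145, one-sided alpha 0.025 (z = 1.9600), power 80% (z = 0.8416), allocation 1:1, 10% loss, 280 randomised. The minimum of 256 completers is in the synopsis and in 9.2.

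**Formula.** n = V × ((z_alpha + z_beta) / (p1 − p2 − δ))², where V is the variance term.

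- Denominator: 0.65 − 0.63 + 0.145 = 0.165.
- Factor at one-sided 0.025: ((1.9600 + 0.8416) / 0.165)² = 288.3.
- Factor at one-sided 0.05 (SAP 3.10): 227.1.

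| Variance term | V | n at 0.025 | n at 0.05 |
|---|---|---|---|
| Standard, p1(1−p1) + p2(1−p2) | 0.65×0.35 + 0.63×0.37 = 0.4606 | 132.8 → 133 | 104.6 → 105 |
| As it appears in the text, p1(1−p2) + p2(1−p2) | 0.65×0.37 + 0.63×0.37 = 0.4736 | 136.5 → 137 | 107.6 → 108 |
| As it appears, arm labels exchanged | 0.63×0.35 + 0.65×0.35 = 0.4480 | 129.2 → 130 | 101.7 → 102 |

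Other variants at 0.025 also miss 128: pooled variance 133, rounded z values 133, 63% in both variance terms 135, 65% in both 132, Farrington–Manning 132, continuity correction 145, and δ taken literally as +0.145, 232.

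**Is 128 credible as a simulation result?** Yes. With 1000 simulations the Monte Carlo standard error near 80% is √(0.8 × 0.2 / 1000) = 1.3 points. Exact power at 128 per arm is 79.2% for a Newcombe limit and 78.8% for a Wald limit, both within one standard error of 80%. By exact Newcombe power, 130 per arm gives 79.8% and 131 gives 80.4%, so 80% is first reached at 131.

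**Losses.**

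- 280 × 0.9 = 252 completers, 126 per arm; 256 − 252 = 4 short.
- 280 secures 256 only if losses are at most 280 − 256 = 24, and 24/280 = 8.6%.
- Keeping 128 per arm at 10% loss needs 128/0.9 = 142.2, so 143 per arm (286 in all). By comparison, 128 × 1.1 = 140.8.
- If the standard term is confirmed, 133 per arm is 266 completers, which 280 gives only at losses up to (280 − 266)/280 = 5.0%.

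**Power at 65% v 63%.** Normal approximation: Φ(0.165 / √(0.4606/n) − z). Exact: binomial enumeration of the event that the Newcombe lower limit exceeds −0.145.

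| Per arm | One-sided 2.5%: normal / exact | Two-sided 90% CI: normal / exact |
|---|---|---|
| 126 | 77.9% / 78.9% | about 86% / 87% |
| 128 | 78.5% / 79.2% | 86.6% / 87.4% |
| 140 | 82.0% / 82.7% | 89.1% / 89.9% |

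**The case against.** The strongest reply is that little changes. The four missing completers cost about 0.3 points of exact power (79.2% at 128, 78.9% at 126). Under the two-sided 90% interval rule in Protocol 9.1.2 and SAP 4.1.2 there is no shortfall at all. This stands and limits the weight of the point. But 9.2, the synopsis and the nQuery table all size the trial at one-sided 2.5%, and one-sided 5% does not return 128 either.

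Other replies hold in part:

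- **The 137 may be an artefact** of a misprinted or misread subscript. That is fair, but the standard term still gives 133.
- **The synopsis gives 10% as an upper bound,** so 252 is its worst case. Section 9.2, however, takes 10% as the expected loss and derives 280 from it.
- **The main analysis is ITT, not completers.** Section 4.2.4.6 says: "Visit 2 procedures will be applied for the visit of premature discontinuation", so some patients who discontinue may still contribute a sore-throat score. But 5.3.1.1 accepts a phone contact if the patient refuses to attend, and the main analysis does not replace missing data. At 10% loss, 126 and 140 per arm are therefore bounds for the number analysed, not a forecast.
- **Completion according to protocol is stricter than not dropping out.** SAP 3.2 also removes patients from the PP set for deviations. A loss of 8.6% or less is thus necessary for 256 but not sufficient.
- **One could randomise 286 instead.** That would preserve 256 at 10% loss, but the power at stake is too small to require it.

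**Conclusion.** The point holds on both counts. On the protocol's own inputs the formula gives 133 per arm with the standard variance term, no reading tested gives 128, and the statement that formula and nQuery agree is wrong. At the loss that 9.2 expects, 280 randomised leaves 252 completers, four below the stated minimum.

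The size is modest. At one-sided 2.5%, power is about 1 to 2 points under 80% at 126 to 128 per arm, and above 80% if all 140 are analysed. Under the 90% interval rule it stays above 80% throughout.

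These figures rest on true rates of 65% and 63%, δ = −0.145 as in the null hypothesis, and Newcombe limits for the exact calculation. The nQuery table names no interval method, but Wald limits lead to the same conclusion. The section should be corrected because its figures do not reproduce, not because the trial is too small.

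**What to change.** Keep 280 randomised. In Protocol 9.2 and the synopsis:

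1. Check the variance term against the cited source formula, then replace 128 as the formula result with the value it gives (133 with the standard term).
2. Delete the claim that the two calculations agree, and report 128 only as the simulation-based nQuery result.
3. State that 10% loss from 280 leaves 252 completers (126 per arm), in place of a 256 minimum that 280 secures only at losses up to 8.6%.
4. Once the one-sided 2.5% in 9.2 and 9.3 is reconciled with the 90% interval rule, state power at 65% v 63% as a range from 126 to 140 per arm: about 78 to 83% at one-sided 2.5%, or about 86 to 90% under the 90% interval rule.

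The cost is wording only, with no extra patients and no design change. Step 1 needs one look at the source; step 4 waits for the alpha decision.

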### 9.3 Applicable significance level

All statistical analyses in this trial will be conducted at 95% significance level (a threshold p value for confirmation of statistical significance is below 0.05), except for the primary endpoint where an one-sided statistical criterion will be used with 97.5% significance level (a threshold p value is below 0.025). The two-sided statistical criteria will be used for all other parameters.

For the primary endpoint evaluation, 90% CI will be calculated for the proportions difference with further evaluation of its lower boundary limit.

#### 9.4 Trial termination criteria

The trial may be terminated under conditions described in Section 4.6 of this protocol.

#### 9.5 Accounting for missed, unanalyzable, and questionable data

During the monitoring visits to the trial sites, the clinical trial specialists (monitors) authorized by the Sponsor will analyze eCRFs for the data completeness. In the case of absence of data on CRFs and availability of relevant information in the primary documentation, questions for investigators and regulations to address inconsistencies will be formulated. At the database check, the expert in statistics authorized by the Sponsor and the data control and processing managers will analyze the trial results for questionable, missed, and unanalyzable data, which might be the basis for the questions for investigators. If possible, the investigators will eliminate the errors identified in CRFs and inform the Principal Investigator and authorized representatives of the Sponsor hereof. In case the identified data errors cannot be eliminated after the completion of the patients participation in the trial, an analysis of the resulting parameter sensitivity to questionable data will be conducted in the statistical analysis.

Information about the missed, questionable, and unanalyzable data will be summarized in the final clinical trial report.

The main analysis for the primary endpoint will be conducted without replacement for the missed, questionable, or unanalyzable data. An additional analysis will be conducted with the data replacement (last observation carried forward); in this case, the last known TSS score will be carried to all subsequent control points.

All other data will be analyzed based on actually available information only, without data replacement.

#### 9.6 **Procedures for reporting any deviations from the original statistical plan**

All deviations from an initial statistical plan must be described and justified in a protocol amendment and/or a final trial report (in the last case, a statistical analysis plan developed before the start of a final statistical analysis must contain a list of those deviations with justification for the reasons thereof).

#### 9.7 Selection of subjects for analysis

The following data sets will be used for analysis:

• The intention-to-treat (ITT) population: all randomized subjects who have received at least one dose of the study drug/placebo and have completed at least one visit aimed at evaluation of the efficacy parameters (i.e., at least all the procedures of Visit 1).

According to the ICH E9 requirements, the ITT population will be considered to be a population for statistical analysis in the equivalence trials (including non-inferiority trials).

- The per protocol (PP) population: all randomized subjects who have completed participation in the trial in accordance with the protocol (have completed the prescribed period of treatment and follow-up without significant deviations from the protocol).
- The safety population (safety): all randomized subjects who received at least one dose of the trial/reference drug and have completed at least one visit to the evaluation of the parameters of safety (i.e., at least all the procedures of Visit 1). As distinct from ITT population, the safety population will be analyzed depending on actually received treatment (not only prescribed) (in case of difference between the prescribed and received therapies).

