# 4.2.2 Trial design flowchart

# 4.2.3 Trial procedures

# 4.2.3.1 Trial procedures in a table form

#### Table 1. Visit schedule

Trial period	Screening/Randomization/Therapy initiation	Treatment		Further follow-up 	Unscheduled visits
Visits	Visit 1	Visit 2  Visit 3 		Visit 4	
Day after initiation of therapy	Day 1	Day 4 Day 5		Day 6/7	
Trial procedures					
Signing of the Informed Consent Form	•				
Demographic data (date of birth, sex, age)	•				
Measurement of weight and height	•				
Medical history	•				
Collection of complaints, actualization of anamnesis	•	•	•		•
Records on the concomitant therapy	•	•	•		•
Evaluation of the throat pain intensity according to VAS by a patient	•	•	•		
Fill-in of TSS questionnaire 	•	•	•		•
Physical examination (including topical examination)	•	•	•		•
Measurement of vital signs 	•	• *	•		•
Hematology 	•	• *	•		
Biochemistry 	•	• *	•		
Urine pregnancy test 	•				
12-lead ECG	•	• *	•		
Evaluation of inclusion/non-inclusion criteria	•				

<sup>1 A follow up visit will be held in the form of a phone contact with the patient to reveal the possible AEs.

<sup>2 In case of premature discontinuation, the follow-up procedures are the same as those at Visit 2.

<sup>3 Only for the Group B patients who did not meet the recovery criteria (total  $TSS \le 2$ ) at Visit 2 (Day 4) and continued the therapy.

<sup>4 Fill-in of TSS questionnaire by the Investigator (scores for every question should be summarized to obtain a total TSS score).

<sup>5 Systolic blood pressure (mm Hg), diastolic blood pressure (mm Hg), breathing rate (per minute), pulse rate (beats per minute), axillary body temperature (°C).

<sup>6 Hb, RBC, WBC with differential, ESR—at the trial site laboratory.

<sup>7 Total protein, AST, ALT, total bilirubin.

<sup>8 For women with the preserved childbearing potential only.

Trial period	Screening/rand omization/ther apy initiation	Treatment		Further follow-up 	Unscheduled visits
Visits	Visit 1	Visit 2 	Visit 3 	Visit 4	
Day after initiation of therapy	Day 1	Day 4	Day 5	Day 6/7	
Trial procedures					
Randomization	•				
Dispensing of the study drugs	•				
Dispensing of the patient's diaries	•				

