# 4.2.4.3 Trial completion visit for Group B patients (Visit 3, Day 5)

This visit is for Group B patients only (ANTI-ANGIN® FORMULA) who did not achieve the recovery criteria (total TSS  $\leq$  2) at Visit 2 (Day 4)

Visit 3 is conducted on Day 5; the patient must visit the trial site in the fasted state and bring the filled-in diary and unused drug.

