# 4.2.4.4 A follow-up visit (Visit 4)

A follow-up visit shall be conducted by phone to find out about the patient's state and any AEs. A visit 2 days after the therapy completion visit (e.g., on Day 6 or 7, depending on the arm and therapy duration).

Follow-up visit procedures (by phone):

• Evaluation of adverse events (without the throat and pharynx examination).

In case of adverse events, the patient might be invited to visit the trial site.

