#### 7.2 Methods and timing for evaluation, recording, and analysis of efficacy parameters

The methods for efficacy criteria evaluation are described in Section 4.2.3.2. The first endpoint is evaluated in the morning at Visit 2 (Day 4, after 3 days of the trial therapy) before the study drugs intake. Other efficacy endpoints are evaluated in terms stated in Section 7.1.

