### 9.1.2. Analysis of the primary efficacy endpoint

The primary outcome measure in this trial was the proportion of patients without sore throat after 3 days of therapy, on Day 4, as evaluated by the Investigator according to the Tonsillopharyngitis Severity Score (TSS), in both Angal and ANTI-ANGIN® FORMULA arms.

A null hypothesis of this trial assumes that Angal, the study drug, is less effective than ANTI-ANGIN® FORMULA, the comparator drug. An alternative hypothesis of this trial assumes that Angal, the study drug, is not less effective than ANTI-ANGIN® FORMULA, the comparator drug.

14.5% is chosen as a non-inferiority margin (see Section 9.2 for a justification) based on the results of a randomized, placebo-controlled trial of a similar drug.

The group comparison will be carried out using the Fisher's exact test (one-sided test, in connection with the null hypothesis of non-inferiority).

For the proportion difference, the 90% confidence interval (CI) will be calculated according to the procedure described in Newcombe, Robert G. "Interval Estimation for the Difference Between Independent Proportions: Comparison of Eleven Methods," Statistics in Medicine, 17, 873-890 (1998).

Thus, the non-inferiority will be confirmed if the limit of the two-sided 90% confidence interval for the difference in the proportions will be 14.5% or lower.

A primary endpoint analysis will be conducted both for the ITT (main analysis) and PP populations (additional analysis).

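### Per-protocol status depends on steps after the Day 4 endpoint, and one of them, the Day 5 visit, exists only for unrecovered comparator patients

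*Protocol*

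**What the plan says.** - **PP set.** Protocol 9.7, repeated in SAP 3.3, limits PP to randomized subjects who "have completed the prescribed period of treatment and follow-up without significant deviations from the protocol".
- **Primary endpoint.** Protocol 9.1.2 defines it as "the proportion of patients without sore throat after 3 days of therapy, on Day 4", rated by the investigator on the sore-throat item of the TSS. On timing, Protocol 7.2 says "The first endpoint is evaluated in the morning at Visit 2", before that day's drug intake.
- **Visit 3 (Day 5).** Protocol 4.2.4.3 says "This visit is for Group B patients only". A footnote to Table 1 gives the condition: "Only for the Group B patients who did not meet the recovery criteria", recovery being a total TSS of 2 or less. Under Protocol 4.2.4.2, every Group A patient, whatever the Day 4 score, returns drug and diary at Visit 2.
- **Visit 4.** Protocol 4.2.4.4 describes a phone call for both arms, "on Day 6 or 7, depending on the arm and therapy duration", whose only listed procedure is adverse-event evaluation.
- **Role of PP.** The primary endpoint is analysed in ITT (main) and PP (additional): Protocol 9.1.2, SAP 3.3 and SAP 4.1.2.
- **Deviations.** The SAP 3.2 table of serious deviations lists neither a missed Visit 3 nor a missed Visit 4. The final list is to be compiled before the analysis starts.

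**The concern.** A PP set for an endpoint measured on Day 4 should depend on what happened up to Day 4. Here the completion clause reaches past the endpoint, and one later step has three unwelcome features together: it follows the endpoint, it is triggered by a Day 4 result on the same questionnaire, and it exists in one arm only. A Group B patient with total TSS above 2 who attends Visit 2 and then misses Visit 3 fails the clause as written. A Group A patient with the same Day 4 score has no Visit 3 to miss.

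If the patients lost this way are mainly sore-throat failures, the comparator's PP response rate is pushed up and the PP difference moves against Angal. ITT and PP could then disagree because of the visit schedule and not because of treatment. Separately, a missed safety call would discard a complete Day 4 rating in either arm, for a reason that has no bearing on the endpoint.

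**Working it through.** **Inputs from Protocol 9.2.** Comparator 63%, Angal 65%, margin 14.5 points, one-sided 2.5%, 128 completed patients per arm, stated power 80%. Protocol 9.1.2 specifies a Newcombe interval for the difference, at the two-sided 90% level, so both levels are shown.

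**Plan's own figure.** Exact binomial enumeration of the Newcombe lower limit at 128 per arm gives power 79.2% at one-sided 2.5%, in line with the stated 80%. With the 90% interval it is 87.4%.

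**Assumptions not in the documents.** Let k be the number of comparator patients rated on Day 4 who then miss Visit 3, and s the share of them with no sore throat on Day 4. The documents give neither. Losses are taken from the 128 in Group B, with no matching loss in Group A.

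Comparator PP rate = (0.63 × 128 − s·k) / (128 − k) = (80.64 − s·k) / (128 − k).

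**All lost patients are failures (s = 0)**

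| k | Comparator PP rate | Angal − comparator | Power, one-sided 2.5% | Power, 90% CI |
|---|---|---|---|---|
| 0 | 63.0% | +2.0 | 79% | 87% |
| 1 | 80.64/127 = 63.5% | +1.5 | 77% | 85% |
| 3 | 80.64/125 = 64.5% | +0.5 | 71% | 82% |
| 5 | 80.64/123 = 65.6% | −0.6 | 66% | 75% |
| 8 | 80.64/120 = 67.2% | −2.2 | 56% | 66% |

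**A quarter are responders (s = 0.25)**

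| k | Comparator PP rate | Power, one-sided 2.5% |
|---|---|---|
| 3 | (80.64 − 0.75)/125 = 63.9% | 74% |
| 5 | (80.64 − 1.25)/123 = 64.5% | 72% |
| 8 | (80.64 − 2.00)/120 = 65.5% | 66% |

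**Break-even.** The comparator rate stays at 63% when s = 0.63, since (80.64 − 0.63k)/(128 − k) = 0.63. Above that share the tilt reverses and favours Angal.

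**Trigger against endpoint.** Visit 3 depends on total TSS and the endpoint on one item, so the two groups overlap without coinciding:

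- Sore throat 0, swallowing 1, hyperemia 2: total 3, a responder who must attend Visit 3.
- Sore throat 1, all else 0: total 1, a failure with no Visit 3.

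**Loss in both arms.** If each arm loses 8 failures, the difference is (83.20 − 80.64)/120 = +2.1 points. Power is 80% at one-sided 2.5% and 87% with the 90% interval, so balanced loss does essentially no harm to the comparison.

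**The case against.** The strongest reply is that little hangs on this. ITT is the main analysis, nothing in the plan makes PP success a condition for claiming non-inferiority, and the likely tilt works against the sponsor's product. That stands, and it limits the seriousness of the point.

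A reader might infer that only comparator failures can drop out of PP. The documents do not support that. The Visit 4 call applies to both arms, and the exclusion criteria (Protocol 5.3.1) and the SAP 3.2 deviations can remove patients, failures included, from either arm. Only the Visit 3 route is specific to the comparator.

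A reader might also infer that nearly everyone sent to Visit 3 is a primary-endpoint failure. No distribution of Day 4 total TSS is given, so this has no source. In the reference trial tabulated in Protocol 9.2, 27 of the 39 active-arm patients (27 + 11 + 1) still sore on Day 4 were rated mild, and some patients of that kind could total 2 or less and never reach Visit 3. The tilt remains plausible, because sore throat counts towards the total and a responder needs at least 3 points from the other items, but it is not certain.

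It can be said, too, that a missed Visit 3 or 4 is not a listed PP exclusion, and that Protocol 11.3 treats a follow-up visit outside its time limits as a minor, logistic deviation. That rule does not plainly cover a contact that never took place, and the completion clause stands apart from the table. The table adds a further possible route: more than 3 missed doses removes a patient from PP, and a Group B patient who skips Day 5 forgoes up to 6 lozenges. Protocol 6.3, however, says that the lower margin of compliance is not evaluated, so those two passages need reconciling. In an open trial with the final list still to be written, silence leaves these decisions to people who may know both arm and outcome.

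Finally, the 128 per arm are already defined as completers, with 10% discontinuation allowed for. That covers some loss of precision, but not a loss that depends on outcome in one arm.

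**Conclusion.** The point holds as a flaw in the PP rule. Followed as written, it conditions a prespecified analysis of the primary endpoint on a later event that depends on outcome and exists in one arm only. The change should be made, but the main conclusion does not turn on it.

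The direction is against Angal if fewer than about 63% of those lost at Visit 3 are free of sore throat. The size cannot be taken from the documents. Under the assumptions above (128 per arm, 1 to 8 comparator patients lost, all failures, no matching Angal loss), PP power at one-sided 2.5% falls from 79% to between 77% and 56%, or from 87% to between 85% and 66% with the 90% interval. The fall is smaller if some of those lost are responders, and there is none through this route if nobody misses Visit 3. These are illustrations and not forecasts.

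A reader might take this as a threat to the validity of a non-inferiority claim. It is not: PP is supportive, and the rule does not raise the risk of a false non-inferiority finding in the main ITT analysis.

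**What to change.** In Protocol 9.7 and SAP 3.3, define the PP set for the primary endpoint as patients who were randomized, were treated, had the TSS rated on Day 4, and had no serious deviation up to that rating. Add that a missed Visit 3 or Visit 4 does not remove a patient from this set and affects only the endpoints measured at those visits. Make the final deviation list in SAP 3.2 follow the same cut-off for this endpoint.

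The cost is wording in two documents, with no new data and no change to visits or treatment. The one downside is that the PP set for the primary endpoint, which may be slightly larger, is no longer identical to the set of full completers, so the report must describe the two separately.
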